10.2. Appendix 2: Time & Events

10.2.1. Protocol Defined Time & Events

Procedures	Pre-Screen	Screen/ Run-in	Treatment Period 1			Treatment Period 2			Early Withdrawal Visit	Follow- up Phone Call
	Visit/Contact	0	1	2 ¹² Randomization	3	4 ^{12, 14}	5 ¹²	6		
Week		-4	0	0	2	4	4	6		7
Treatment Day		-26 to -30 days	0	1 ¹⁸	14 (-2/+2) days	28 (-2/+2) days	29 ¹⁸	42 (-2/+2) days		47 to 51 days
Written Informed Consent	X									
Genetics Consent	X ¹									
Subject Demography	X									
Medical History (including CV)		X								
Disease (Asthma) History		X								
Medication History	X	X								
Smoking history/status		X								
Inclusion/Exclusion Criteria		X								
Evidence of EIB		X								
Efficacy Assessments										
Spirometry (full FEV ₁ and FVC)		X	X ²	X ²	X ²	X	X ²	X ²	X	
Exercise Challenge Testing (Treadmill)			X ^{3, 17}	X ⁴	X ⁵		X ⁴	X ⁵		
Post-Challenge Serial FEV ₁ Measurements			X ³	X ⁶	X ⁶		X ⁶	X ⁶		
Asthma Control Questionnaire-5			X		X	X		X	X	
Dispense SenseWear ¹⁵ accelerometer		X								
Collect SenseWear accelerometer								X	X	
Safety Assessments										

CONFIDENTIAL

201832

Procedures	Pre-Screen	Screen/ Run-in	Treatment Period 1			Treatment Period 2			Early Withdrawal Visit	Follow- up Phone Call
Visit/Contact	0	1	2 ¹² Randomization	3	4 ^{12, 14}	5 ¹²	6	7 ^{12, 14}		
Week		-4	0	0	2	4	4	6		7
Treatment Day		-26 to -30 days	0	1 ¹⁸	14 (-2/+2) days	28 (-2/+2) days	29 ¹⁸	42 (-2/+2) days		47 to 51 days
Concomitant Medication	X	X	X	X	X	X	X	X	X	X ⁷
Physical Examination		X								
Vital Signs		X	X ⁸	X ⁸	X ⁸	X	X ⁸	X ⁸	X	
12-lead ECG		X								
Adverse Event Assessment	X ⁹	X ⁹	X	X	X	X	X	X	X	X
Issue Medical Conditions Diary Card		X	X		X	X				
Review Medical Conditions Diary Card			X ¹⁰	X	X ¹⁰	X ¹⁰	X	X ¹⁰	X	
Laboratory Assessments										
Genetics Saliva Sample			X ¹							
Urine Pregnancy Test		X	X			X			X	X ¹³
Investigational Product										
Dispense Fluticasone Propionate		X			X					
Collect Fluticasone Propionate			X			X				
Dispense Rescue ¹⁶ Albuterol/salbutamol		X	X	X	X	X	X			
Collect Rescue Albuterol/salbutamol			X		X	X		X		
Dispense IP			X ¹¹			X				
Assess study drug compliance			X	X	X	X	X	X	X	
Collect IP					X			X	X	

1. Genetics saliva sample collected at Visit 2 (following Randomization) or at any scheduled visit thereafter. Genetics consent MUST be obtained PRIOR to collection of the Genetics sample.
2. Pre-exercise spirometry (full FEV₁ and forced vital capacity (FVC) testing), conducted immediately pre-exercise (and after vital signs), if applicable. Subject should have withheld albuterol/salbutamol within previous 6 hours.
3. Performed for determination of eligibility. Serial spirometry performed 5, 10, 15, 30, 45 and 60 minutes post- exercise challenges. Subjects must demonstrate a decrease in FEV₁ of $\geq 20\%$ at one time point within 30 minutes of the end of a standardized exercise challenge.
4. Exercise challenge testing will be performed at 23 hours following the evening study treatment doses given at Visit 2 and Visit 5
5. Exercise challenge testing will be performed at 12 hours and 23 hours following the evening study treatment doses given at the beginning of Visits 4 and 7.
6. Serial spirometry performed at time points 5, 10, 15, 30, 45 and 60 minutes post- exercise challenges. Longer monitoring may be required for those subjects who do not return to 95% of baseline FEV₁ values within 60 minutes.
7. Concomitant medications collected for adverse events only between end of treatment and follow-up phone contact.
8. Vital signs will be collected before (prior to the pre-exercise spirometry) and after each exercise challenge test.
9. Adverse Event and Serious Adverse Events to be collected from the start of study Drug (Visit 1) until the follow up contact. However, any SAE related to study participation will be recorded from the time of Informed Consent
10. Review medical conditions diary card, including an assessment of any potential change in exercise capacity
11. An unblinding card will be dispensed along with double blind IP.
12. Subjects will be contacted by telephone 8-9 days prior to Visits 2, 4, 5 and 7 and reminded to wear the SenseWear accelerometer for the 7 days preceding these visits.
13. Pregnancy test will be conducted via home test kit and results will be reported at the Follow-up phone contact.
14. Visit 4 and Visit 7 will begin between 5PM and 11PM and continue over a period of approximately 24 hours. Subjects will return to the clinic at 12 hours (± 1 hour) and 23 hours (± 1 hour) (after the evening dose of study medication from the evening visit) for an exercise challenge procedure.
15. Subjects will be contacted by telephone 8-9 days prior to Visits 2, 4, 5 and 7 and reminded to wear the SenseWear Armband accelerometer for the 7 days preceding these visits.
16. Collect and re-dispense rescue as needed from Visit 1
17. Subjects who achieve a decrease in FEV₁ of 15% to $< 20\%$ may continue taking their daily run-in medication and repeat the eligibility exercise challenge and associated procedures **once** within a week of the original procedure.
18. Visit 3 must be performed on the day immediately following Visit 2. Visit 6 must be performed on the day immediately following Visit 5.

10.3. Appendix 3: Assessment Windows

Clinic visits are scheduled to take place as specified in Section [10.2.1](#). Individual measurements will be reported based on the visits and planned relative times they are assigned to in the study database without adjustment.

If a circumstance should arise where multiple measurements have been collected and recorded against the same time point, then the first valid value will be used for that time point.

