8.3. Efficacy

8.3.1. Spirometry

Subjects should abstain from drinking beverages with high caffeine content such as tea or coffee for 4 hours prior to the spirometry procedure.

FEV₁ should be measured using spirometry equipment that meets or exceeds the minimal recommendations of the American Thoracic Society (ATS)/European Respiratory Society (ERS) [[Miller](#), 2005]. All sites will use standardized spirometry equipment provided by an external vendor. Full FEV₁ and FVC will be conducted at Visit 1, and pre-dose at Visit 5, and prior to each exercise challenge at Visits 2, 3, 4, 6 and 7.

For full FEV₁ and FVC testing at Screening and at randomisation (Visit 2), at least two valid and two repeatable (with no more than 8) efforts should be obtained using ATS/ERS guidelines. For all other visits where full FEV₁ and FVC testing is performed (prior to each exercise test at visits 3, 4, 6 and 7), at least two valid efforts should be

obtained. At each time point, the largest FEV₁ and FVC should be recorded, even if they do not come from the same effort.

Serial FEV₁ measurements only (not FVC) will be conducted serially as described in Time and Events Table [Table 3](#) following each exercise challenge at Visits 2, 3, 4, 6 and 7.

Subjects must have a FEV₁ of at least 70% of their predicted normal value to be eligible to take part in the study at Visit 1.

After Visit 1, subjects will always be required to withhold their albuterol/salbutamol for at least 6 hours before each clinic visit.

Subjects must not administer study drug prior to coming to the clinic on study visit days.

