8.3.3.2. Visit 2 (Randomization)

Treatment period 1 baseline FEV₁: Visit 2 begins between 5 PM and 11 PM and should begin at approximately the same time as Visit 1 (± 1 hour). Spirometry will be performed at Visit 2 at approximately the same time as at Visit 1 (± 1 hour). The FEV₁ should be measured approximately 12 hours (± 1 hour) after dosing with run-in medication (FP 250 mcg). At least two valid and two repeatable spirometry efforts should be obtained before the first exercise challenge.

From this spirometry testing, the target FEV₁ values #2 and #3 (Section 8.3.1.1) should be determined based on the pre-exercise FEV₁.

Eligibility Exercise Challenge: After the pre-exercise baseline FEV₁ has been determined, an exercise challenge will be performed according to the method described in the SRM.

Post-exercise Serial Spirometry: Following the eligibility exercise challenge, serial spirometry (FEV₁) will be performed at 5, 10, 15, 30, 45 and 60 minutes post-exercise.

To qualify for randomization, subjects must demonstrate a decrease in FEV₁ of $\geq 20\%$ when compared to the FEV₁ obtained immediately pre-exercise for at least one of the post-exercise spirometry efforts obtained within 30 minutes post-challenge. Subjects who achieve a decrease in FEV₁ of 15% to $< 20\%$ may continue taking their daily run-in medication and repeat the eligibility exercise challenge **once** within a week. In the event where a repeat visit is required for the exercise challenge, spirometry and vital signs measurements will be performed pre- and post- exercise challenge as detailed in [Table 3](#). In addition, ACQ-5 and a review of concomitant medication and adverse events will be performed at the repeat visit.

Dosing: Eligible subjects will administer their evening dose of double-blinded study medication following the eligibility exercise challenge/serial spirometry. Evening dosing should occur between 5 PM and 11PM.

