10.5.2. Baseline Definition & Derivations

10.5.2.1. Baseline Definitions

In general, the subject level baseline (or study baseline) is defined as the value taken at visit 2 (randomization), and the period level baseline is defined as the pre-treatment value taken at the start of each treatment period (visit 2 and visit 5). Using these definitions the period baseline for treatment period 1 is the same as the subject level baseline.

For FEV₁ and Vital Signs, the baseline value at visit 2 will be taken from the “Pre Challenge” planned time.

The primary analysis will include as a covariate, the period baseline value as well as including as a covariate, the mean of the two period baseline values.

For the physical activity measures assessed by the biosensor, the period baseline will be derived using all the available data from the last 7 calendar days prior to, but not including the first clinic visit of the treatment period (Visit 2/5). For example, if the randomisation visit (Visit 2) was on the 18th May then the period baseline for treatment period 1 would be derived as the average of the non-missing data that is available from the 11th May to the 17th May inclusive.

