
 Reporting for tables, figures and formal statistical analyses : 
 Planned time will be used in figures, summaries, statistical analyses and calculation of any derived parameters, unless otherwise stated. Reporting for Data Listings: 
 Planned and actual time will be shown in listings (Refer to IDSL Statistical Principle 5.05.1). Unscheduled or unplanned measurements will be presented within the subject's listings. 		
Unscheduled Visits		

 Unscheduled visits will not be included in summary tables or figures. All unscheduled visits will be included in listings. 		
Descriptive Summary Statistics		
Continuous Data	Refer to IDSL Statistical Principle 6.06.1	
Categorical Data	N, n, frequency, %	

Reporting Standards
Graphical Displays

• Refer to IDSL Statistical Principals 7.01 to 7.13.• The programs for statistical analysis tables will create SAS datasets with the unrounded numbers from the statistical models to be used in any graphs. This will include all LS means, standard errors, treatment differences or ratios and confidence intervals. This will be done for all analysis tables regardless of whether or not a figure is planned as part of SAC.• The programs for all graphical displays will additionally create a CSV file with the final data that is used in the graph in order to allow the graph to be redrawn for any potential publication requirement in the future.

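### SAP 10.3 keeps the first valid value with no exception for the repeated Visit 2 challenge, so a non-qualifying attempt could become the study and Period 1 baseline

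*SAP*

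**What the plan says.** Protocol 6.2.1 and 8.3.3.2 require a fall in FEV₁ of at least 20% within 30 minutes of the Visit 2 challenge. A fall of 15% to under 20% allows one repeat within a week. Protocol 8.3.3.2 continues: "In the event where a repeat visit is required for the exercise challenge, spirometry and vital signs measurements will be performed" before and after the challenge, and ACQ-5 is completed again. In the Time and Events table the repeat has no column of its own; it is footnote 17 on the Visit 2 exercise cell.

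SAP 10.3 says that measurements are "reported based on the visits and planned relative times they are assigned to in the study database without adjustment". When one time point holds several stored results, its rule is "then the first valid value will be used for that time point".

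On baseline, SAP 10.5.2.1 says that "the subject level baseline (or study baseline) is defined as the value taken at visit 2 (randomization"), and makes the Period 1 baseline the same value. It adds: "For FEV₁ and Vital Signs, the baseline value at visit 2 will be taken from the" pre-challenge planned time. Protocol 10.4 takes the baseline as the FEV₁ measured before treatment when each period begins, at Visit 2 or Visit 5. SAP 10.5.3 says: "Unscheduled visits will not be included in summary tables or figures". None of these sections mentions the repeat challenge.

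**The concern.** A subject who qualifies on the repeat has two complete Visit 2 data sets up to seven days apart. The first failed the entry criterion; the second led to randomisation and first dose. A technically good test with a 17% fall is still valid: the only FEV₁ values that SAP 10.1.1 sets to missing in both analysis populations are those labelled unacceptable. So if both sets carry the Visit 2 label, the stated rule keeps the wrong one.

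For those subjects the Period 1 baseline would predate first dose by up to a week, while the Period 2 baseline comes from the dosing visit (Protocol 8.3.3.5). At stake are the endpoints computed from period baseline (maximal decrease and serial change in FEV₁, ACQ-5 change and the 0.5-point improvement), the vital-signs change in Table 3.28, and the study-baseline lung function displays in Tables 1.29 to 1.31. In those displays some randomised subjects could appear with a fall below the 20% entry threshold.

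**Working it through.** **1. The plan's own figure.** Inputs from Protocol 10.2.1: difference 5, within-subject SD 8, 56 evaluable subjects, two-sided 5%. Standard error = 8 × √(2/56) = 1.51; noncentrality = 5/1.51 = 3.31; with 54 degrees of freedom, power = 90.1%, as in Table 5. Also 66 × 0.85 = 56.1. No input depends on which Visit 2 value is baseline, so neither figure moves.

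**2. Outcome by database label.**

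| How the two attempts are stored | Baseline that results | Route |
|---|---|---|
| Both as Visit 2, pre-challenge | Non-qualifying first attempt | SAP 10.3 |
| First as Visit 2, repeat as unscheduled | First attempt in summary tables and figures | SAP 10.5.3 |
| Repeat as Visit 2, first elsewhere | Qualifying repeat | No conflict |

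The documents do not state the label.

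**3. Outcome the definitions intend.** Dosing follows the qualifying challenge (Protocol 8.3.3.2). Visit 3 falls on the day after Visit 2 and 23 hours after the dose given there (Table 3, footnotes 4 and 18). Baseline is the value at the start of the period (Protocol 10.4), at the visit that SAP 10.5.2.1 calls randomization. For a repeater, all of these point to the repeat. The first two rows of the table contradict them.

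**4. Primary and secondary endpoints.** SAP 10.6.3 defines the primary endpoint as 100 × (pre-exercise − minimum)/pre-exercise, using the pre-exercise value from that same challenge. Period baseline enters only as a covariate. The secondary endpoints have the same structure.

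The effect on the primary endpoint was illustrated by simulation with assumed inputs:
- repeat share 10%, 25% or 50%;
- mean FEV₁ 3 L, visit-to-visit CV 5% or 10%, no systematic difference between attempts;
- baseline slope 0 or 10 points per litre;
- 56 subjects, 1,500 trials per setting.

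Replacing the qualifying value by the first value had these largest effects:
- mean estimate: −5.037 to −5.051, a shift of 0.014 points;
- standard error: 1.522 to 1.570;
- power: 90.4% to 89.2%.

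**5. Endpoints from period baseline.** For linear changes (litres, ACQ-5 score), the period baseline is also a covariate. Subtracting it from the outcome only shifts its own coefficient by −1, so the treatment difference again depends on it only through the covariate. What moves directly is the raw summaries and the adjusted mean changes. The percent decrease from period baseline and the 0.5-point ACQ-5 improvement are not linear in baseline and change subject by subject. For example, with an assumed minimum of 2.40 L, a baseline of 3.00 L gives 100 × 0.60/3.00 = 20.0%; a stored baseline 5% lower (2.85 L) gives 100 × 0.45/2.85 = 15.8%.

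**6. Mean baseline fall (Table 1.30).** Understatement = repeat share × (repeat fall − first fall). The first fall is taken as 17.5%, the midpoint of 15% to 20%. Shares and repeat falls are assumed.

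| Share of randomised subjects | Repeat fall 20% | 25% | 30% |
|---|---|---|---|
| 10% | 0.25 | 0.75 | 1.25 |
| 25% | 0.62 | 1.88 | 3.12 |
| 50% | 1.25 | 3.75 | 6.25 |

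Entries are percentage points.

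**7. Day 0.** Per-protocol deviation 6 (SAP 10.1.1) counts days from Visit 2. If the first attempt's date were used and the repeat came 7 days later, a 12-hour challenge on true day 10 would be counted as day 17 and escape the rule. The 7-day biosensor baseline and period day use the same date.

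**The case against.** The strongest reply is that the definitions already settle the matter. Baseline is tied to the randomization visit and to the start of the treatment period, and for a repeater that can only be the repeat day. A data manager who stores the repeat as Visit 2 gets the right baseline and SAP 10.3 is never triggered. This stands as a statement of intent. It does not close the gap, because the result would rest on a labelling choice that neither document records, while the SAP's stated rule points the other way if the labels coincide.

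Some stronger readings are tempting, but the documents do not support them:
- A reader might infer that the failed test becomes baseline for every repeater, however the data are stored. The third row of the label table is the counterexample.
- A reader might take SAP 10.5.3 to put the first attempt into the models. It covers only tables and figures, and does not say how covariates are derived.
- A reader might see a clash with Protocol 8.3.1: "At each time point, the largest FEV₁ and FVC should be recorded". That sentence governs what is recorded, so normally one value per time point reaches the database.
- A reader might conclude that Table 1.30 would show subjects as ineligible. Eligibility deviations are reported from the eCRF (SAP 4.1). The displayed fall also uses values to 60 minutes against 30 for eligibility, so a first attempt could still reach 20%.

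It is also fair that the affected endpoints lie outside the testing hierarchy, and that the first attempt was made on the same continued run-in medication.

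**Conclusion.** The gap is real and conditional. SAP 10.3 can select the non-qualifying attempt as study and Period 1 baseline, and nothing in the SAP prevents it; whether it does depends on database labels that the documents do not give.

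The effect on the primary result is negligible: about 0.01 points on the estimate and about 1 point of power in the illustration, even with half the subjects repeating. The same is expected for the secondary endpoints, where period baseline is also only a covariate; they were not simulated. No stated sample size or power changes.

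The effect on the period-baseline endpoints, vital-signs change and Tables 1.29 to 1.31 is direct for repeaters. Its size cannot be fixed from the documents: the 0.25 to 6.25 points for mean baseline fall rest wholly on assumed repeat shares and falls. Sequence is randomised, so the treatment comparison mainly gains noise, while the description of the randomised population could be wrong. This should be corrected before unblinding because the remedy is specific and nearly free.

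**What to change.** Add to SAP 10.5.2.1: *For subjects who repeat the Visit 2 challenge, all Visit 2 baselines (pre-challenge FEV₁, serial FEV₁, vital signs and ACQ-5) and the Visit 2/day 0 date are those of the qualifying repeat, that is, the last set before the first double-blind dose.* Exempt this case from the first-valid-value rule in 10.3 and from the unscheduled-visit exclusion in 10.5.3. Keep the first attempt in the listings, and report the number of subjects who qualified on a repeat.

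The cost is one sentence, two cross-references, one programming rule and a check of how the repeat is labelled in the database. Data collection, sample size and the primary model stay as they are.

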10.4. Appendix 4: Treatment States

10.4.1. Treatment States

Assessments and events will be classified according to time of occurrence relative to the start and/or stop date of the study treatment. The earliest and latest exposure treatment start and stop dates will be used to determine whether an assessment or event was pre-treatment, on-treatment or post-treatment. If it is not possible to tell whether an assessment or event was on-treatment or not it will be considered as on-treatment.

10.4.1.1. Treatment States for Concomitant Medications

A medication will be summarized in every classification (pre/during/post) in which it was taken, so a medication that was started in the run-in and stopped during treatment will appear in both the pre-treatment and the during treatment tables.

Medications will be classified by comparing the start date and end dates of the medication to the dates of the first and last doses of study medication within the treatment periods using the following definitions:

Treatment State	Definition
Pre-Treatment	Date medication taken \leq first dose date of the study
During Treatment	First dose date of treatment period + 1 \leq date medication taken \leq last dose date of treatment period
During Treatment (washout)	Last dose date of treatment period + 1 \leq date medication taken \leq first dose date of next treatment period
Post-Treatment	Date medication taken \geq last dose date of study + 1

10.4.1.2. Treatment States for Adverse Events and Severe Asthma Exacerbations

Treatment states for adverse events are described below. Severe asthma exacerbations will be treated in the same way, with the exacerbation start date used in place of the AE start date.

Treatment State	Definition
Pre-Treatment	AE start date \leq first dose date of the study -1
On-Treatment	First dose date of treatment period \leq AE start date \leq last dose date of treatment period + 1
Post-Treatment	AE start date \geq last dose date of study + 2 OR Last dose date of treatment period + 2 \leq AE start date \leq first dose date of next treatment period - 1

AEs occurring during the washout period or during the follow-up period are therefore classified as post-treatment and will be summarized under the treatment from the previous period.

Note: Time Since 1st Dose will be derived as follows:

- If the First Dose Date or the AE Onset Date are missing then => missing
- If First Dose Date > AE Onset Date then => AE Onset Date – First Dose Date
- If First Dose Date \leq AE Onset Date then => AE Onset Date - First Dose Date +1

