8.3.3.4. Visit 4 and Visit 7 (Blinded Treatment Exercise Challenges)

Visit 4 and Visit 7 begin between 5 PM and 11 PM and are conducted over approximately 24 hours. Subjects will be required to attend three clinic visits during each 24-hour period for Visit 4 and Visit 7. The evening visit should begin at approximately the same time as Visit 1 (± 1 hour).

Dosing: At the beginning of Visit 4 and Visit 7, subjects will administer their evening doses of double-blinded study medication in the clinic and the time of dosing will be recorded. In addition to administering the evening dose, vital signs will be measured and a review of concomitant medication and AEs performed.

Subjects will return to the clinic 12 (± 1) hours and 23 (± 1) hours after evening dosing for exercise challenge testing.

Pre-exercise FEV₁: At least two valid spirometry efforts with full FEV₁ and FVC maneuvers should be obtained just prior to each exercise challenge.

From this spirometry testing, the target FEV₁ values #2 and #3 (Section 8.3.1.1) should be determined based on the pre-exercise FEV₁.

Exercise challenge testing: Exercise challenge testing will occur at 12 (± 1) hours and 23 (± 1) hours after administering the evening dose. (The 12-hour exercise challenge and spirometry measurements should occur prior to dosing of the study medication).

Post-exercise Serial Spirometry: Following the eligibility exercise challenge at each visit, serial spirometry (FEV₁) will be performed at 5, 10, 15, 30, 45 and 60 minutes post-exercise.

Washout Medication Dosing: At the end of Visit 4, the washout medication should be dispensed and first evening dose administered following completion of the 23-hour post evening dose exercise challenge/serial spirometry, and prior to the subject's leaving the clinic.

8.3.3.5. Visit 5

Treatment period 2 baseline FEV₁: Spirometry will be performed at Visit 5 at approximately the same time as at Visit 1 (± 1 hour). The FEV₁ should be measured approximately 12 hours (± 1 hour) after dosing with the washout medication. At least two valid spirometry efforts should be obtained.

Dosing: Subjects will administer their evening doses of double-blinded study medication following the spirometry.

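### SAP 10.4.1.2 counts the whole first-dose date as on-treatment, so adverse events from the Visit 2 qualifying exercise challenge, which precedes the first double-blind dose, are tabulated under FF/VI or FP

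*SAP*

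**What the plan says.** **Adverse events.** SAP 10.4.1.2 ends the pre-treatment state the day before the first dose: "AE start date \leq first dose date of the study -1". The on-treatment state takes in the whole first-dose date, "First dose date of treatment period \leq AE start date", and closes the day after the period's last dose. AEs in washout or follow-up are post-treatment and are reported under the preceding period's drug.

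**General rule.** SAP 10.4.1 orders events against the treatment start and stop dates. It sends an event to on-treatment when its state cannot be determined.

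**Visit 2.** Protocol 8.3.3.2 starts the visit between 5 PM and 11 PM and fixes the sequence: "Eligible subjects will administer their evening dose of double-blinded study medication following the eligibility exercise challenge/serial spirometry". Dosing falls in the same 5 PM to 11 PM band.

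**Visit 5.** Protocol 8.3.3.5 has no challenge: "Subjects will administer their evening doses of double-blinded study medication following the spirometry".

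**Concomitant medications.** SAP 10.4.1.1 treats the same date the other way. Pre-treatment is "Date medication taken \leq first dose date of the study", and the during-treatment state opens a day later: "First dose date of treatment period + 1 \leq date medication taken".

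**Collection and display.** AEs are collected from the start of run-in (Protocol 8.4.1.1). The main on-treatment tables count them by treatment whatever their cause (SAP 8.2.1).

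**The concern.** A date-only rule is usually harmless. Here the protocol schedules a provocation test on the first-dose date, shortly before the dose, in every randomised subject. Protocol 5.6.1 names the risks of that test: bronchoconstriction, cardiovascular stress, musculoskeletal injury and falls. An event from it is collected, dated to the first-dose date and counted against a double-blind treatment not yet taken.

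The SAP also treats the same challenge as baseline elsewhere. Its FEV₁ results are summarised as study baseline in Tables 1.29 and 1.30, while an AE from it is on-treatment.

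Adverse events are the only safety endpoint listed (Protocol 4.4). At stake is whether the on-treatment AE rates of a small trial describe what happened after dosing.

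**Working it through.** The plan states no figure on this point, so there is none to reproduce. The check applies the two date rules to the visit timeline.

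**1. Pre-dose hours on the Visit 2 date.** Inputs: earliest start 17:00 and latest dosing 23:00 (Protocol 8.3.3.2); 10 minutes of exercise and a last FEV₁ at 60 minutes (Protocol 8.3.2).

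- Earliest dose: 17:00 + 0:10 + 1:00 = 18:10, before allowing for vital signs and pre-exercise spirometry.
- Latest dose: 23:00.
- Pre-dose part of the date: about 18.2 to 23 hours.

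**2. Rules applied.** D is the first-dose date. Dose times of 18:15, 20:00 and 23:00 were assumed, and all three give the same result.

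| Item | State under the SAP |
|---|---|
| AE at 08:00 on D | On-treatment, Period 1 drug |
| AE 65 minutes before the dose on D, at or just after the challenge | On-treatment, Period 1 drug |
| Medication taken on D only | Pre-treatment |
| AE at a non-qualifying challenge on an earlier date | Pre-treatment (correct) |

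**3. Share of the window.** Day 0 is Visit 2. With the last dose on Day 14, the window is Days 0 to 15, which is 16 dates or 16 × 24 = 384 hours. With the last dose on Day 15 it is 17 dates or 408 hours.

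- Lowest: 18.2 / 408 = 4.5%.
- Highest: 23 / 384 = 6.0%.

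This is a share of clock time, not of events.

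**4. Effect on the comparison.** Let q be the probability that a randomised subject has a pre-dose AE on D. The documents give no value. Randomised drug has not yet been taken, so q is the same in both sequences. With 1:1 allocation, half the subjects take each drug in Period 1. Each drug's rate therefore rises by at most about q/2 (less where the subject has another on-treatment AE). If the true rates are a and b, then (a + q/2) − (b + q/2) = a − b, so the simple difference is roughly unchanged. A ratio would move towards 1, but none is planned.

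**5. Sensitivity of the frequency cut-off.** With at most 66 subjects per drug, 2/66 = 3.03%. If the 3% cut-off for Tables 3.6 and 3.13 is applied within treatment, which the SAP does not state, two subjects are enough to list a term.

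**6. Visit 5.** Events earlier that day occur on washout FP but are charged to the Period 2 drug. Applying the SAP's post-treatment rule instead would report them under the Period 1 drug. In the FF/VI-then-FP sequence, that charges FF/VI about two weeks after its last dose.

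**The case against.** The strongest defence is that the rule is a disclosed, cautious default. AE dates are complete or missing (SAP 10.7.2.1), no onset-time rule is described, and over-counting is the safe direction for a safety table. That stands for events whose order is unknown. It does not stand for a challenge event, because the protocol fixes the challenge before the dose.

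Other points that limit the reach and stand:

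- Expected symptoms of the disease under study are not AEs unless more severe than expected (Protocol 13.5.1), so ordinary exercise-induced symptoms do not enter.
- A subject whose challenge leads to exclusion is never dosed and has no first-dose date.
- Drug-related tables depend on the investigator's causality assessment.
- Subjects allocated to FP were already on the same FP regimen in run-in. For them the event precedes double-blind treatment but not exposure to FP.
- The SAP already derives time since first dose, which identifies first-dose-date AEs. It does not separate before from after the dose.

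A reader might infer more than the documents support:

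- **Bias against one drug.** Allocation is 1:1 and the challenge precedes randomised drug, so the expected effect is equal.
- **A distorted exacerbation table (3.24).** Severe exacerbations are collected only from randomisation or first receipt of investigational product (Protocol 8.4.2), so this table is barely touched.
- **A quarter of events affected.** One of the four challenges in the Period 1 window is pre-dose, against none of three in Period 2. These are counts of challenges, not of AEs.
- **All of Tables 3.2 to 3.15 inflated.** Tables 3.5 and 3.12 are post-treatment displays.
- **A broad clash with concomitant medications.** Study albuterol/salbutamol is not recorded in the eCRF (Protocol 7.1, 7.10), and a drug continued past the date appears in both states. The mismatch is visible only for one-day treatment with another drug.

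**Conclusion.** The point holds as a misclassification of known direction and modest reach. AEs from the qualifying Visit 2 challenge, and any others in the roughly 18 to 23 hours before the first double-blind dose, are counted as on-treatment. Both drugs' on-treatment AE rates are inflated, mainly in Period 1, with no expected advantage to either. The number of events is unknown.

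This assumes that the first double-blind dose is taken on the date of the qualifying challenge, as the protocol directs, and that no onset time enters the classification, since the SAP describes none. It also reads the SAP's first dose of the study as the first double-blind dose. The SAP should say so, because the protocol also calls run-in FP study treatment. The on-treatment rule itself does not depend on that reading.

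**What to change.** 1. In SAP 10.4.1.2, class an AE starting on the Period 1 first-dose date as pre-treatment when its onset is known to precede the first double-blind dose, from an onset time or a before/after-first-dose tick. Keep the on-treatment default when the order cannot be determined.
2. If no field can be added, flag first-dose-date AEs in Listing 11 and repeat Table 3.2 without them.
3. For Visit 5, flag pre-dose events and show them separately as occurring on washout FP. Do not move them to the previous period's treatment.
4. Align SAP 10.4.1.1 with this, or explain why its during-treatment state starts at "First dose date of treatment period + 1".

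The cost is SAP wording plus one eCRF field, or one flag and one repeat table. There is no added burden on subjects.
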